The Importance of Assessing Suicide-Related Outcomes. Although the treatment target of BCBT is suicidal ideation and behavior, we will also assess psychiatric distress and suicide-related thoughts to characterize the sample and explore any ancillary treatment effect. It is important to assess concomitant treatments in any treatment outcome study to provide a context for interpretation of study results. In addition, assessment of service utilization will provide a confirmation of patient engagement with continuing care as well as indicate whether or not crisis services (ED, psychiatric readmission) were accessed.

Specific Aims/Hypotheses

As a pilot feasibility open trial, this study is not powered for statistical significance. However, we outline our predictions here in relation to descriptive statistics and/or effect sizes.

Aim 1: To describe the feasibility, acceptability, and tolerability of app-enhanced BCBT. Feasibility will be assessed using enrollment rates as well as a qualitative assessment of treatment implementation barriers and patient and clinician feedback. Acceptability will be assessed using the Client Satisfaction Questionnaire and app-user feedback. We expect that participants will continue to engage with the treatment after discharge via the SmartPhone App, as assessed using the Utility of Techniques Questionnaire and utilization data (e.g., number of times accessed) collected by the app. Tolerability will be assessed using rates of discontinuation and adverse events. We predict that descriptive data will demonstrate good feasibility, acceptability, and tolerability.

Aim 2: To collect initial descriptive pilot data and BCBT effect size estimates from pretreatment through follow-up for reducing suicidality and improving other suicide-related-outcomes. We predict that participants will demonstrate a large reduction in suicidal ideation from pretreatment to each follow-up assessment as evidenced by a Hedges' g of 0.8 (large effect) or greater. Effect sizes for changes in suicide-related outcome measures (psychiatric distress, suicide-related cognitions, service utilization) will also be explored. We predict that descriptive data will show low levels of suicidal behavior and psychiatric readmission over follow-up. For exploratory purposes, we will also assess other types of service utilization over follow-up (e.g., outpatient, ED visits).

Research Design

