Sampling. We will enroll 4 young adults (ages 18-24) admitted for inpatient treatment with a history of suicide attempt (lifetime) and active ideation (with or without plan or intent) on admission who own and have access to their phone (iPhone or Android with capability to

download apps) during their inpatient stay. Admission will be defined as admission to either the medical floor (in cases where medical stabilization was required following a suicide attempt) or to the psychiatric inpatient unit (in cases where medical stabilization was not required). Suicide attempt will be defined as self-directed behavior that results in injury or the potential for injury, and in which there was evidence, whether implicit or explicit, of intent to die. Inclusion criteria will also include ability to understand the nature of the study and provide written informed consent, willing and able to provide at least two verifiable contacts for emergency or tracking purposes, and expected length of stay long enough to complete the entire treatment protocol. Participants will be excluded if they are not fluent in English, are experiencing current mania or psychosis, have lifetime history of schizophrenia spectrum disorder, intellectual disability, or organic brain illness, if the inpatient treatment plan includes detox protocol or electroconvulsive therapy, or any other psychiatric or medical condition that in the investigator's opinion would preclude informed consent or participation in the trial. Participants who are not fluent in English will be excluded given that at least some assessments are available in English only, the research is utilizing an app only available in English and treatment is not validated using a translator. We expect that all enrolled participants will complete at least one treatment session; however, if there is attrition prior to completing at least one treatment session we will continue to enroll additional participants until we meet this target sample.

Measures. The Measurement Schedule is outlined in Table 1 and measures are detailed below.

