Diagnoses. Diagnostic status will be assessed at pre-treatment using the Diagnostic Interview for Anxiety, Mood, and Obsessive-Compulsive and Related Disorders (DIAMOND, Tolin et al., 2018) a semi-structured interview for DSM-5 psychiatric disorders. The DIAMOND assesses for a wide range of DSM-5 disorders, which will allow for determining diagnostic inclusion/exclusion criteria as well as characterization of the study sample. In addition, symptoms of borderline personality disorder will be assessed using the McLean Screening Instrument for Borderline Personality Disorder (MSI-BPD, Zanarini et al., 2003). The MSI-BPD is a 10-item self-report measure that has demonstrated good sensitivity and specificity in detecting symptoms of borderline personality disorder. Diagnoses will also be extracted from the medical record.

Demographic and Health Status. Demographic information will be obtained from the medical record and through self-report. Participants will also complete a self-report measure indicating the presence of chronic medical conditions.

Suicidal Behavior. Suicidal behavior will be assessed using the Columbia Suicide Severity Rating Scale (C-SSRS), a widely used suicide assessment measure (Posner et al., 2011). The lifetime version of the C-SSRS will be administered at pre-treatment to assess both the total number of behaviors ever present as well as the number of behaviors present during "the past month." At subsequent assessments the "since last visit" version will be administered. The behavior scales of the C-SSRS have demonstrated sensitivity to change across treatment, sensitivity and specificity in identifying lifetime actual and interrupted attempts (Posner et al., 2011), and predictive validity for identifying future suicidal behaviors and rehospitalization (Greist et al., 2014; Horwitz et al., 2015). Documented incidences of suicide attempt will also be extracted from the medical record.

Suicidal Ideation/Intent. Suicidal ideation and intent will be assessed using the severity and intensity subscales of the same C-SSRS versions and timeframes as described above (Posner et

Table 1. Measurement Schedule.

	Intake	Treatment	Discharge	1mo	2mo	3mo
DIAMOND	X					
Demographic Form	X					
Health Form	X					
MSI-BPD	X					
C-SSRS	X		X	X	X	X
ASIQ	X		X	X	X	X
DASS-21	X		X	X	X	X
SCS	X		X	X	X	X
DTS	X		X	X	X	X
DERS	X		X	X	X	X
Wish to Live\Wish to Die	X	X	X	X	X	X
Reasons for Living\Dying	X	X	X	X	X	X
AE Assessment	X	X	X	X	X	X

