Implementation Barriers	X	X	X	X	X	X
Utility of Techniques		X	X	X	X	X
System Usability Scale		X	X	X	X	X
Qualitative Feedback		X	X	X	X	X
CBT Compliance Measure		X				
Client Satisfaction			X	X	X	X
Service Utilization/CSI			X	X	X	

al., 2011). Suicidal ideation will also be assessed using the Adult Suicidal Ideation Questionnaire (ASIQ, Reynolds, 1991), a 25-item self-report scale. The ASIQ has demonstrated moderate positive correlations with depression, hopelessness, and past suicide attempts, good internal reliability, and good test-retest reliability (Reynolds, 1991). Suicidal ideation/intent will also be assessed through self-reported intensity of Wish to Live and Wish to Die (0 = “*Not at all*” to 8 = “*Very Much*”) and listing and rank ordering by importance up to five reasons for living and reasons for dying (Jobes & Bonanno, 1995).

Psychiatric Symptoms. Psychiatric distress symptoms will be assessed using the 21-item Depression Anxiety Stress Scales-21 (DASS-21, Henry & Crawford, 2005). The DASS-21 has demonstrated good internal consistency across scales, and good convergent validity with other measures (Henry & Crawford, 2005). Psychiatric distress tolerance will be assessed using the Distress Tolerance Scale (DTS, Simons & Gaher, 2005). The DTS is a 15-item self-report measure assessing the degree to which individuals experience negative emotions as intolerable

(e.g., “When I feel distressed or upset, all I can think about is how bad I feel”). The DTS has evidenced good reliability and internal consistency in clinical samples (Hsu et al., 2013). The Difficulties in Emotion Regulation Scale (DERS, Gratz & Roemer, 2004) is a 36 item self-report measure of 6 facets of emotion regulation including awareness, clarity, impulsivity, goal-directed behavior, non-acceptance, and strategies for feeling better (e.g. “When I’m upset, I believe there is nothing I can do to feel better.”). Items are rated on a scale from 1 to 5 (*almost never* to *almost always*) with higher scores indicated greater difficulty with emotion regulation. The DERS has demonstrated high internal consistency, good test-retest reliability, and adequate construct and predictive validity (Gratz & Roemer, 2004).

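### Minor: a C-SSRS effect size from intake to discharge would compare a past-month rating with one covering only the stay, and the Analytic Plan does not exclude it

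*Combined protocol and SAP*

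**What the plan says.** All references are to the combined protocol and SAP.

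**C-SSRS windows.** For intake, Measures (Suicidal Behavior) states: "The lifetime version of the C-SSRS will be administered at pre-treatment". It covers both the whole lifetime and the past month. Every later assessment uses the since-last-visit version. These windows are written for behaviors, and the next subsection, Suicidal Ideation/Intent, extends them: "Suicidal ideation and intent will be assessed using the severity and intensity subscales of the same C-SSRS versions and timeframes as described above".

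**Timing.** Table 1 schedules the C-SSRS at intake, discharge and 1, 2 and 3 months, with none during treatment. Procedure allows up to four sessions, usually one a day but flexibly, and lets the discharge assessment be done by phone if the patient leaves first. Sampling requires an expected stay long enough for the whole treatment. No length of stay in days is given.

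**Other ideation measures.** The same subsection adds: "Suicidal ideation will also be assessed using the Adult Suicidal Ideation Questionnaire". It continues: "Suicidal ideation/intent will also be assessed through self-reported intensity of Wish to Live and Wish to Die", and also lists "listing and rank ordering by importance up to five reasons for living and reasons for dying".

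**Effect size.** Aim 2 says: "We predict that participants will demonstrate a large reduction in suicidal ideation from pretreatment to each follow-up assessment", with a Hedges' g of at least 0.8 as the mark. The Analytic Plan computes g for suicidal ideation from intake to post-treatment and through follow-up. It names no measure, no C-SSRS subscale and no C-SSRS baseline window.

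**The concern.** Table 1 has no post-treatment visit other than discharge, so the planned intake-to-post-treatment contrast ends there. The C-SSRS is the first-listed ideation measure and nothing excludes it. If it is used with its stated timeframes, the baseline looks back about a month and the discharge score looks back only to intake.

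A rating that picks up the worst point in its window tends to be higher when the window is longer. The contrast would then show improvement even if ideation had not changed. Effect-size estimates are an explicit product of Aim 2, so a systematic shift in one of them matters although no test is planned.

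**Working it through.** The plan has no figure of its own to reproduce here. N = 4 is a feasibility choice and 0.8 is a prediction.

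**1. Windows read from the text**

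| Visit | C-SSRS window | Approximate length |
|---|---|---|
| Intake | lifetime; past month | 30 days for the shorter one |
| Discharge | since intake | the gap; not stated, probably days |
| 1 month | since discharge assessment | 30 days if on time |
| 2 and 3 months | since previous visit | 30 days if on time |

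Only the discharge window is clearly unequal. If the discharge assessment is done 7 or 14 days late, the 1-month window shrinks to 30 − 7 = 23 or 30 − 14 = 16 days.

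**2. Model (assumed; the documents give no SD, correlation or scoring rule)**

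Daily ideation is a person effect, N(0, 1), plus a within-person fluctuation with SD s and day-to-day correlation 0, 0.5 or 0.8. There is no true change. The score is the worst day in the window. With M(w) the score over w days,

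g = [mean M(30) − mean M(w)] / √{[var M(30) + var M(w)] / 2},

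so positive g means apparent reduction.

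**3. Hand check at correlation 0, 7-day gap**

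The maximum of 30 independent standard normals has mean 2.04 and variance 0.25. The maximum of 7 has mean 1.35 and variance 0.39. Hence

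g = s(2.04 − 1.35) / √[1 + s²(0.25 + 0.39)/2] = 0.69s / √(1 + 0.32s²).

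- s = 0.25: 0.1725 / 1.010 = 0.17
- s = 0.5: 0.345 / 1.039 = 0.33
- s = 1.0: 0.69 / 1.149 = 0.60

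**4. Simulated large-sample g, range over correlations 0 to 0.8 (simulation error about 0.01)**

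| s | 4 days | 7 days | 10 days | 14 days | 30 days |
|---|---|---|---|---|---|
| 0.25 | 0.25–0.27 | 0.17–0.20 | 0.12–0.15 | 0.08–0.11 | 0.00 |
| 0.5 | 0.48–0.53 | 0.33–0.38 | 0.24–0.29 | 0.16–0.20 | 0.00 |
| 1.0 | 0.85–0.91 | 0.60–0.65 | 0.44–0.49 | 0.30–0.35 | 0.00 |

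The correlation-0 results agree with step 3. If the score is the window average, g is 0 to within 0.01 at every gap. If ideation is constant within a person, it is 0. Stronger fluctuation gives more: at a between-person variance share of 0.3 (s = √(0.7/0.3) = 1.53), the 7-day figure is 0.80 to 0.84.

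**5. Follow-up visits.** Windows of 23 and 16 days at 1 month give 0.03 to 0.12 and 0.07 to 0.28. On-time visits give about 0.

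**6. Four people, coarse scale.** Assume a 0–5 score with one level per between-person SD, clipped at the ends, and baseline mean 2.5 to 4. With a 7-day gap, g is positive in 0.50–0.60, 0.74–0.81 and 0.89–0.91 of trials at s = 0.25, 0.5 and 1.0. With equal windows it is positive in 0.18–0.40. The rest are negative or exactly zero; ties at 7 days occur in 34–46%, 15–21% and 6–8% of trials.

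**The case against.** **It is conditional at every step.** No text says that the C-SSRS supplies g, that ratings take the worst point, or how long patients stay. If the ASIQ is meant, or scores average over the window, there is no C-SSRS artefact. This stands, and it is why the size is an illustration. It does not remove the point: the timeframes are stated, the contrast is planned, and nothing keeps the two apart.

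**Little turns on it.** Four people, one arm, no test, and no threshold attached to discharge. This also stands and caps the severity. The statement that the study is not powered answers significance testing; it does not make two different look-back periods comparable.

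**A reader might infer that the 0.8 prediction is compromised.** The documents do not support that. Aim 2 ties it to each follow-up assessment, and those windows are about a month, like the past-month baseline.

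**A reader might infer that a lifetime baseline is planned.** The lifetime rating is collected and not excluded, but no text uses it for change.

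**A reader might infer that the artefact almost fixes the sign of g.** A continuous-score simulation gives a positive g in about 95% of four-person trials at 7 days, against 50% with equal windows. The documents do not establish a tie-free score. On the assumed six-level score, ties are common and the figures are those in step 6 of the working.

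**Conclusion.** The point holds and is minor. Any C-SSRS ideation g from intake to discharge would compare unequal windows, and the Analytic Plan does not prevent it. With no true change, the shift is about 0.17 to 0.65 for a 7-day gap and 0.08 to 0.35 for 14 days. On an assumed six-level score with four people and a 7-day gap, g would be positive in about 50% to 90% of trials, against 18% to 40% with equal windows.

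These figures assume worst-point scoring, fluctuating ideation, a 30-day baseline, and within-person SD 0.25 to 1.0 times the between-person SD. The documents state none of these apart from the past-month window.

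Matching the windows would not turn g into a treatment effect. Entry requires "active ideation (with or without plan or intent) on admission" and there is no control arm, so recovery from the admission crisis remains in every contrast.

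**What to change.** Add to the Analytic Plan:

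> For any C-SSRS ideation effect size, the past-month intake score is the baseline; lifetime scores are not used for change. C-SSRS Hedges's g is computed against the 1-, 2- and 3-month visits only. The discharge C-SSRS is reported descriptively with the days it covers. The intake-to-discharge ideation g uses a measure whose rating period is the same at both visits (the ASIQ total, if its form has a fixed recall period, with Wish to Die as supportive), named before data are examined. If data have already been examined, the choice is labelled as made afterwards. The ASIQ recall period is stated alongside the result.

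The documents do not give the ASIQ recall period, so it must be read from the form.

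**Cost.** Wording only: no visit, rating or measure changes. One C-SSRS effect size, intake to discharge, is no longer reported. A fixed ASIQ recall longer than the stay would overlap the period already rated at intake and could dilute change at discharge. That works against finding improvement rather than creating it, and stating the recall period lets the reader judge it.

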Session 1. In session 1, the patient completes psychoeducation about the “suicide mode,” which is the BCBT case conceptualization model for suicidal behavior. The suicide mode includes baseline risk factors (i.e., factors which predispose or make one vulnerable to suicide) interacting with triggering events leading to acute risk factors (i.e., temporary exacerbations in emotions, thoughts, physiology, and behaviors associated with suicide). The patient will also learn how BCBT targets modifiable aspects of the suicide mode in order to enhance safety. Next, the therapist conducts a narrative assessment asking patients to tell their “story” of the index suicide attempt (i.e., the attempt which preceded current admission) and constructs an individualized suicide mode case conceptualization. At the end of the session, a crisis response plan is developed, which involves identifying warning signs, self-management strategies, supportive friends or family members, and professional resources which could be accessed if needed in a crisis.

Sessions 2. The primary goal of Session 2 is to increase cognitive flexibility and ambivalence toward suicide by focusing attention on positive aspects of living. Two interventions are introduced. First, the therapist introduces reasons for living by asking patients to describe reasons why they do not want to die and what prevents them from making another suicide attempt. For example, relationships with family, to enjoy pleasures such as certain foods or experiences, or to be alive during important future events are common reasons for living. The reason for living is reinforced through a visualization exercise focusing on vivid and specific details to increase emotional salience and improve access from memory. For the second intervention, the patient creates a virtual “hope kit” by identifying items that could serve as concrete visual reminders of positive experiences. The rationale for choosing each item is reviewed by the therapist in order to discourage inclusion of any potentially iatrogenic items.

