Session 3. Session 3 focuses on counseling on reducing access to lethal means. This is an essential component to preventing death by suicide. Because activations of the suicide mode are temporary, creating barriers to lethal means can create a window of opportunity for suicide distress to subside and/or for the patient to enact a crisis response plan. Even if the patient makes a suicide attempt, doing so with a less lethal method still improves the patient’s chances of surviving. During session 3 access to means, including access to firearms, is assessed and a plan developed to restrict means. Common examples of means restriction are to remove firearms from the home or to have a family member lock up and dispense medications. The means restriction plan is shared with the unit clinician. In this session the therapist also introduces virtual coping cards to modify cognitive factors of the suicide mode. The coping cards provide a concrete memory aid.”

Session 4. In the final session, the therapist reviews all previous skills and reinforces the app as a reference to use after discharge. Two relapse prevention tasks are completed as well. The participant is directed to imagine the index suicide episode as well as a hypothetical future suicidal episode. For each, the therapist guides the participant to imagine him- or herself utilizing one or more skills learned in BCBT to effectively manage the situation. In addition, anticipated high risk situations are identified and any necessary changes to the crisis response plan are made. The therapist discusses the upcoming discharge and reviews specific ways that practicing skills can be integrated into daily life.

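### Can Session 1 be delivered to a participant whose suicide attempt did not lead to the current admission?

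*Combined protocol and SAP*

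**What the plan says.** The Sampling paragraph of Research Design sets the target: "We will enroll 4 young adults (ages 18-24) admitted for inpatient treatment". The attempt and ideation criterion is "history of suicide attempt (lifetime) and active ideation (with or without plan or intent) on admission". An attempt is defined by behaviour and intent ("Suicide attempt will be defined as self-directed behavior that results in injury or the potential for injury", with evidence of intent to die), and the definition has no element of timing. Admission has two routes. The medical floor is one, used "in cases where medical stabilization was required following a suicide attempt". The other route makes no mention of an attempt: "to the psychiatric inpatient unit (in cases where medical stabilization was not required".

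The Session 1 description has the patient tell the story of "the index suicide attempt (i.e., the attempt which preceded current admission", after which the therapist "constructs an individualized suicide mode case conceptualization". Session 1 also contains psychoeducation about the suicide mode and a crisis response plan.

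The Session 4 description uses a slightly different term: "The participant is directed to imagine the index suicide episode as well as a hypothetical future suicidal episode". It does not define that episode.

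The opening of the Treatment section says that the sessions follow the protocol of the group's ongoing randomised trial, with the app added. That protocol is not part of these documents.

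**The concern.** The eligibility rule and the Session 1 text seem to have different patients in mind. The rule explicitly accepts a lifetime attempt and ideation without plan or intent. Session 1 appears to assume that an attempt brought the patient into hospital. For someone admitted with ideation only, the natural reading of the index attempt has no referent, and no alternative is given. Session 4 does not resolve this, because its term is broader and undefined.

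In a feasibility study the delivered treatment is what is being tested. If therapists chose different events for such patients, the participants would receive somewhat different Session 1 and Session 4 content. The ratings of adherence, barriers and satisfaction would then describe a mixed treatment. With 4 participants, one such case is 1/4 = 25% of the sample.

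**Working it through.** The plan states no figure on this point, and Power Analysis gives no calculation for the sample size, so there is nothing to reproduce. The check is a comparison of the texts, followed by one illustration of size.

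**1. Does an index event exist for every eligible participant?**
- Sampling requires at least one lifetime attempt from everyone.
- Session 1 asks for an attempt that came before the current admission. It does not say that the attempt must have caused the admission.
- Taken literally, the Session 1 wording therefore fits every eligible participant. The word *index* favours a narrower reading, so the wording is ambiguous, but the narrative is not shown to be undeliverable.

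**2. How many definitions are there?**
- Sampling states eligibility and defines no index event.
- Session 1 gives one definition.
- Session 4 uses a variant term, undefined, which may mean the same event.
- That makes one definition and one loose term, with no direct conflict between definitions.

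**3. What depends on the event?**

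| Component | Needs an index event? |
|---|---|
| Session 1 psychoeducation | No |
| Session 1 narrative | Yes |
| Session 1 case conceptualization | In part; the suicide mode also covers baseline risk factors and triggers |
| Session 1 crisis response plan | No |
| Session 4 imagined past episode | Yes, under the broader term |
| Session 4 imagined future episode | No |

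**4. How likely is an affected participant?** Let *p* be the share of eligible patients with no attempt tied to this admission. The documents do not give *p*, so the values below are assumptions. With n = 4 from Sampling, and participants taken as independent:

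P(at least one) = 1 − (1 − *p*)^4; expected number = 4*p*.

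| *p* | (1 − *p*)^4 | P(at least one of 4) | Expected number |
|---|---|---|---|
| 0.10 | 0.6561 | 0.344 | 0.4 |
| 0.25 | 0.3164 | 0.684 | 1 |
| 0.50 | 0.0625 | 0.938 | 2 |
| 0.75 | 0.0039 | 0.996 | 3 |

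**5. Does any planned result depend on it?** The Analytic Plan lists:
- descriptive summaries of recruitment and retention, implementation barriers, satisfaction, treatment utilization, adverse events, service utilization and suicidal behaviours;
- Hedges' g for ideation, distress and suicide-related cognitions.

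None of these is defined through the index event. The CBT Compliance Measure, where an effect on adherence would be sought, is not on the list.

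**6. What would an extra flag add?**
- The intake C-SSRS already covers lifetime and past-month behaviour, and documented attempts are taken from the medical record.
- These show when an attempt occurred, though not whether it led to this stay.
- A yes/no split of 4 people gives groups of 0 and 4, 1 and 3, or 2 and 2. No comparison of compliance ratings between such groups would be informative.

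**The case for a change.** The strongest reply is that the parenthesis in Session 1 is there to single out one attempt by its relation to this admission. If any earlier attempt qualified, it would identify nothing for a patient with several. Two therapists could then both follow the text and use different events. The choice could also carry forward, since Session 3 works on cognitive factors of the suicide mode and Session 4 returns to the index episode. Nothing collected records directly whether an attempt led to the stay.

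Much of this stands. The narrower reading is the more natural one, and the documents do not say what to do when it fails. The ongoing trial's protocol may settle the matter, but that cannot be confirmed from these documents, so it counts neither way.

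The step from unclear wording to damaged results does not stand. The CBT Compliance Measure is described as rating the participant's adherence to the session protocol. A participant who narrates an older attempt when asked can still be rated adherent. If the material proves awkward for such a patient, the Implementation Barriers Log and the clinician's feedback on sessions can capture it, and the sessions are audio-recorded. Finding that kind of difficulty is part of what a feasibility pilot is for.

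**Conclusion.** No change to the plan follows. This is a gap in wording, limited to the Session 1 narrative, the conceptualization drawn from it and one Session 4 task. An ideation-only admission among the 4 participants is quite possible (34% to 94% for assumed shares of 10% to 50%), but its consequence for the statistics is nil: no sample size, effect size or listed summary changes. A therapist has an earlier attempt or the present crisis to work from. Which of these is suitable is a clinical matter on which this review takes no view. Reconciling the terms used in Sampling, Session 1 and Session 4 is an editorial matter for the sponsor, and the analysis does not wait on it.

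The conclusion rests on two points: the lifetime-attempt criterion is applied to everyone, and the analysis stays descriptive, without subgroups, as the Analytic Plan sets out. It would need another look if session adherence became a formal outcome or if a larger trial reused this text.
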